19.2 Retention of Records

Essential documents should be retained until at least 2 years after the last approval of a marketing application in an ICH region and until there are no pending or contemplated marketing applications in an ICH region or at least 2 years have elapsed since the formal discontinuation of clinical development of the investigational product. These documents should be retained for a longer period, however, if required by the applicable regulatory requirements or by an agreement with Faraday.

Faraday will notify the Investigator/institution when the study records are no longer needed.

If the Investigator withdraws from the study (e.g., relocation, retirement), the records must be transferred to a mutually agreed upon designee (e.g., another investigator, IRB). Notice of such transfer will be given in writing to Faraday.

The Investigator must inform Faraday immediately if any documents are lost, to be transferred to another facility, or to be transferred to a different owner.

The Investigator must contact Faraday prior to destroying any records associated with the study.

19.3 Confidentiality and Publications

All clinical trial findings and documents will be regarded as confidential. The Investigator and members of his/her research team must not disclose such information without prior written approval from the Sponsor.

The anonymity of participating subjects must be maintained. Subjects will be identified on CRFs and other documents by their subject number, initials and/or birth date, not by name and subject in accordance with local requirements. Documents not to be submitted that identify the subject (e.g., the signed informed consent) must be maintained in confidence by the Investigator.

Faraday is committed to the timely communication of data from clinical research trials, following the Pharmaceutical Research and Manufacturers of America principles. Where possible, authorship will be agreed at the beginning of the study. The authors will form a publication committee and this committee will propose and develop appropriate scientific manuscripts or abstracts from the study data. Investigators may not present or publish partial or complete study results individually. Any manuscript or abstract proposed by the Investigators must be reviewed and approved in writing by Faraday before submission for publication. Names of all Investigators participating in the study will be included in the publication. The publication committee for a study will comprise of authors selected in adherence with the International Committee of Medical Journal Editors criteria for authorship. That is, all authors must meet each of the following 3 criteria:

- Substantial contribution to conception and design or acquisition of data, or analysis and interpretation of data
- Drafted the article or revised it critically for important intellectual content
- Approved the final version for publication

Members of the study steering committee generally fulfill the authorship criteria through their involvement in protocol design and review, monitoring of and sometimes direct involvement with recruitment, and thus they will usually be part of the publication committee. If studies are multicenter, it may be appropriate to assign group authorship.

In addition, certain Faraday employees involved in the design and conception of the protocol, study management and data analysis and interpretation are qualified authors and will be included in the publication committee e.g., the lead physician, statistician and study project manager or their equivalents.

3 ABBREVIATIONS

Abbreviations pertain to the SAP only (not the TFLs).

ADaM	analysis data model
AE	adverse event
AMI	acute myocardial infarction
ANOVA	analysis of variance
ATC	Anatomical Therapeutic Chemical
AUC	area under the curve
AUC _{inf}	area under the concentration-time curve extrapolated to infinity
AUC _{last}	area under the concentration-time curve from time 0 to the time of the last observed quantifiable concentration
AV	Atrioventricular
BLQ	below the limit of quantification
BPM	beats per minute
CDISC	Clinical Data Interchange Standards Consortium
CL	total body clearance
C _{max}	maximum observed plasma concentration
CMR	cardiac magnetic resonance
CRF	Case Report Form
CSR	Clinical Study Report
CV%	coefficient of variation
ECG	electrocardiogram
EDV	end-diastolic volume
EF	ejection fraction
ESV	end-systolic volume
FS	fractional shortening
ICH	International Conference on Harmonisation
INF	infarct size
ITT	intent-to-treat

Kel	apparent terminal elimination rate constant
LLOQ	lower limit of quantification
MedDRA	Medical Dictionary for Regulatory Activities
MRI	magnetic resonance imaging
MSI	myocardial salvage index
NC	not calculated
NR	no result
PCI	percutaneous coronary intervention
PK	pharmacokinetics
PP	per protocol
SAP	Statistical Analysis Plan
SD	standard deviation
STEMI	ST-segment elevation myocardial infarction
T _{1/2}	apparent terminal elimination half-life
TEAE	treatment-emergent adverse event
TFLs	tables, figures, and listings
T _{last}	time of last quantifiable concentration
T _{max}	time when maximal concentration is achieved
V _{ss}	volume of distribution at steady-state
VV	ventricular volume
V _z	volume of distribution during the terminal elimination phase
WHO	World Health Organization

4 INTRODUCTION

This SAP has been developed after review of the clinical study protocol Final Version 1.0 dated 02 April 2017 and Final Version 2.0 dated 21 August 2017.

This SAP describes the planned analysis of the safety, efficacy, and PK data from this study. A detailed description of the planned TFLs to be presented in the Clinical Study Report (CSR) is provided in the accompanying TFL shell document. In general, the analyses are based on information from the protocol, unless they have been modified by agreement between Faraday Pharmaceuticals and Covance Early Clinical Biometrics. A limited amount of information concerning this study (eg, objectives, study design) is given to help the reader's interpretation. This SAP must be finalized prior to the lock of the clinical database for this study. When the SAP and TFL shells are agreed upon and finalized, they will serve as the template for this study's CSR.

This SAP supersedes the statistical considerations identified in the protocol; where considerations are substantially different, they will be so identified. If additional analyses are required to supplement the planned analyses described in this SAP, they may be performed and will be identified in the CSR. Any substantial deviations from this SAP will be agreed upon between Faraday Pharmaceuticals and Covance Early Clinical Biometrics and identified in the CSR.

This SAP is written with consideration of the recommendations outlined in the International Conference on Harmonisation (ICH) E9 guideline entitled, "Guidance for Industry: Statistical Principles for Clinical Trials" and the ICH E3 guideline entitled, "Guidance for Industry: Structure and Content of Clinical Study Reports."^{1,2}

5 STUDY OBJECTIVE AND PURPOSE

The purpose of this study is to evaluate the safety, efficacy, and PK of 3 dose levels of FDY-5301 compared to placebo in ST-segment elevation myocardial infarction (STEMI) patients undergoing percutaneous coronary intervention (PCI).

6 STUDY DESIGN

6.1 Primary Outcomes

The primary outcome for this study will be the combined number and incidence rate of several arrhythmias of interest for 14 days post-study drug. The arrhythmias of interest include the following categories:

- Ventricular fibrillation
- Sustained ventricular tachycardia (heart rate [HR] \geq 125 beats per minute [BPM], \geq 30 seconds)

- Non-sustained ventricular tachycardia (HR \geq 125 BPM, \geq 16 irregular beats, $<$ 30 seconds)
- High degree Atrioventricular (AV) block (2nd or 3rd degree, \geq 8 irregular beats)

The time-to-last-event outcome for each arrhythmia of interest will be studied.

The time-to-patch-applied, derived as time duration between the start of PCI procedure and the application of the patch monitoring device will also be studied.

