4.1 Primary Outcome

The primary outcome for this study will be the combined number and incidence rate of several arrhythmias of interest that occur in each group over a 14 day period post-study drug. These arrhythmias including ventricular fibrillation, sustained ventricular tachycardia (≥ 125 BPM, ≥ 30 seconds), non-sustained ventricular tachycardia (≥ 125 BPM, ≥ 16 beats, < 30 seconds) and high degree AV block (2nd or 3rd degree, ≥ 8 beats) were chosen because they are significant prognostic indicators of depressed left ventricular ejection fraction and cardiac death [1]. The combined number of arrhythmic events in each group will be calculated along with the arrhythmia incidence rate defined as the percentage of patients in each group experiencing at least one of the defined arrhythmias of interest.

An exploratory sub-analysis will be conducted to determine the number and incidence rate of each separate arrhythmia type per dose group.

Continuous cardiac monitoring will occur for 14 days post PCI by means of wearable patch devices.

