11.4.1 Primary Analysis (Safety)

Incidence Rate of Events

The primary outcome for this study will be the combined number and incidence rate of several arrhythmias of interest for 14 days post-study drug. The combined number of arrhythmic events in each treatment group will be calculated along with the arrhythmia incidence rate defined as the number of arrhythmia events of interest divided by the total person-time within each treatment group (or the overall FDY-5301 group), expressed as a percentage. The summarization will be presented by 2 separate periods within the 14-day monitoring duration, and also as overall. Period 1 will be the first 48 hours since the start of PCI and period 2 will be the remaining time of 14-day monitoring duration.

The same summarization method will be repeated after stratification of baseline TIMI flow (grade 1 and lower combined, or, grade 2 and 3 combined) and infarct type (anterior or other).

Person-time is an estimate of the time-at-risk in hours for all patients who contributed to the analysis population. The total person-time is calculated as the sum of recording time across patients during the 14 day monitoring period, within each treatment group (or the overall FDY-5301 group). The unit for person-time in this study is person-hours.

The number of arrhythmias of interest and its incidence rates will be summarized by treatment group and the overall FDY-5301 group.

The incidence rate ratio of each active treatment group (and overall) against the placebo group will be calculated.

As an exploratory sub-analysis, the summarization for the number of events and incidence rates will be repeated separately for each arrhythmia category as outlined in Section 6.1 and also separately for non-serious arrhythmias (ie, any arrhythmias which do not meet the criteria as outlined in Section 6.1).

The arrhythmia incidence rates (ie, arrhythmias per person-time) for each arrhythmia type will be summarized by treatment groups in hourly intervals. The intervals may be altered upon reviewing the actual data. Arrhythmia rates by time interval may also be presented in a graphical format.

Occurrence of reperfusion arrhythmias collected prior to use of the continuous rhythm monitoring device will be summarized according to categories as defined in the CRF.

Relationship between each arrhythmia type occurred within 48 hours of the start of PCI procedure and all-cause mortality may be evaluated depending on data availability.

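### SAP 6.1 counts only 'irregular' beats for NSVT and high degree AV block; the supplied protocol has no such condition, and read literally the SAP would move some protocol-defined primary events into the non-serious summary

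*SAP*

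**What the plan says.** The protocol states the beat thresholds in the synopsis (statistical methods) and in Sections 4.1, 11 and 14.1.3. The criteria are the same each time; Section 4.1 has "non-sustained ventricular tachycardia (≥ 125 BPM, ≥ 16 beats, < 30 seconds) and high degree AV block (2nd or 3rd degree, ≥ 8 beats". None of the four places mentions regularity.

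SAP 6.1 lists the same four arrhythmia categories. For NSVT it asks for at least "16 irregular beats", and for high degree AV block at least "8 irregular beats". Sustained VT is defined by rate and duration only, as in the protocol.

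SAP 11.4.1 uses Section 6.1 as a sorting rule. It plans a separate summary of "non-serious arrhythmias (ie, any arrhythmias which do not meet the criteria as outlined in Section 6.1".

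On precedence, SAP Section 4 says: "This SAP supersedes the statistical considerations identified in the protocol; where considerations are substantially different, they will be so identified". SAP Section 13 lists three changes: the person-time adjustment, the scope of the interim analyses, and the stratified summaries by TIMI flow and infarct location. It lists no change to the event criteria.

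**The concern.** The two documents give different case definitions for two of the four components of the primary outcome. Protocol 14.1.4 sets the primary goal as describing how often these arrhythmias occur over 14 days, and 14.1.6 says that no hypothesis will be tested. The counts and rates are therefore themselves the primary result, and they depend directly on the case definition.

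Read literally, the SAP wording has two effects. A regular run that qualifies under the protocol drops out of the primary tables, and it then appears in a table labelled non-serious in a study whose main focus is safety. A reader who checks SAP 13 for departures from the protocol would not learn of it.

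**Working it through.** The plan gives no figure to reproduce. The primary outcome has no event-rate assumption, alpha or power, so the check is a comparison of texts with one short calculation.

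**Criteria side by side**

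| Category | Supplied protocol | SAP 6.1 |
|---|---|---|
| Ventricular fibrillation | no threshold | no threshold |
| Sustained VT | ≥ 125 BPM, ≥ 30 s | the same |
| NSVT | ≥ 125 BPM, ≥ 16 beats, < 30 s | the same, but beats must be irregular |
| High degree AV block | 2nd or 3rd degree, ≥ 8 beats | the same, but beats must be irregular |

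The word appears only in the two criteria that count beats. Neither document defines it.

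**Which VT runs fall in the gap**

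Duration = beats ÷ rate × 60. At the 125 BPM threshold:

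- 16 beats last 16 ÷ 125 × 60 = 7.68 s.
- 30 s holds 125 × 30 ÷ 60 = 62.5 beats, so a run shorter than 30 s has at most 62.

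A regular run of 16 to 62 beats at 125 BPM therefore meets the protocol's NSVT definition and fails SAP 6.1 read literally. Once the same rhythm lasts 30 s, it counts as sustained VT under both documents. The literal rule is thus inconsistent within the SAP: a regular run is a primary event at 30 s and a non-serious one just below that.

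For AV block there is no upper duration limit. Any regular episode of 8 or more beats meets the protocol and fails the literal SAP wording.

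**Where the difference would carry through**

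- *Count and rate.* SAP 11.4.1 divides events by monitored person-hours. Reclassification removes events from the numerator and leaves the hours unchanged. If a fraction f of a group's primary events is reclassified, both its count and its rate are multiplied by (1 − f).
- *Rate ratio.* The active-to-placebo ratio is multiplied by (1 − f_active) ÷ (1 − f_placebo). It is unchanged if the fractions are equal and shifts if they differ.
- *Time to last event.* A patient whose only events were reclassified would be censored, because SAP 11.4.1 censors patients with no arrhythmia of interest. For other patients the last event could move earlier.
- *Sub-analyses.* The summaries by category, period, TIMI flow and infarct type, and the Kaplan-Meier curves, use the same criteria.

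The documents give no event rates and no split by regularity, so f cannot be calculated. Any percentage quoted for the loss would only repeat the assumed share of regular runs.

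**What is not affected**

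The sample size of 80 (protocol 14.1.4, SAP 9) rests on INF/VV, MSI and troponin AUC. This wording does not touch it.

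**The case against.** The strongest reply is that the word may have been meant loosely, as abnormal beats, meaning the beats that make up the run. The two documents would then say the same thing. The inconsistency at 30 s favours this reading, since nothing suggests that anyone wanted a regularity test for short runs only. This stands as a limit on the consequences, but it does not defend the wording: if the word adds nothing, it should go.

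Second, protocol Section 11 gives the patch recordings to a blinded, standardised central reading whose criteria are not in the documents. If that reader applies the protocol definition and the SAP wording is not used to filter the result, no event moves. This also stands.

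Third, SAP Section 4 says the SAP was written from protocol versions dated 02 April and 21 August 2017. The supplied protocol is dated 30 August 2017, and its Section 5.2 says European sites do not use it. The word could come from a version we do not have. The mismatch with the supplied protocol is certain; that the SAP made an undeclared change is not.

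Fourth, precedence is only partly clear. The SAP supersedes statistical considerations, whereas protocol 4.1 and 11 define the outcome outside the statistics section. However, the definition is repeated in 14.1.3, which is inside it, and SAP 11.4.1 makes Section 6.1 operative whichever document ranks higher.

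Fifth, the affected events would still be reported. SAP 11.4.1 summarises them, protocol 13.1 and SAP 11.5.1 record arrhythmias as adverse events, and seriousness for SAE reporting follows protocol 13.4 and not the title of this table. That is right, and it limits the harm to misclassification.

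**Conclusion.** The point holds as a conflict between the supplied protocol and SAP 6.1 on the case definition for two of the four primary components. The SAP rule is undefined and, taken literally, inconsistent with its own sustained VT criterion. The difference in the texts is certain. Any movement of events is conditional: it requires that the word be applied literally, either in the central reading or when the primary tables are built.

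A reader might infer that every regular run will be lost and that the primary arrhythmia estimate will therefore be wrong. The documents do not support that. They neither define the word nor give the reading criteria, and they plan to report the events that fall outside Section 6.1. The number affected is unknown, and alpha, power and sample size are untouched.

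Correction is still warranted, because the counts and rates are the primary result and two people following the two documents could classify the same recording differently.

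**What to change.** Before database lock, and preferably before the 14-day arrhythmia analysis in SAP 12 (the first to use these criteria), delete the word *irregular* from the NSVT and AV-block bullets of SAP 6.1 so that they match protocol 4.1, 11 and 14.1.3. Confirm that the central reading specification uses the same text.

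If a restriction on regularity is intended, define it in measurable terms, list it in SAP 13 as a change from the protocol, and report the count and rate on the protocol definition alongside the restricted ones. If the word comes from another protocol version, say so in SAP 13 and state which definition governs.

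The preferred change costs two deleted words and one check of the reading specification. It needs no new data, and the sample size stays the same.

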6.2 Secondary Outcome

6.2.1 Secondary Efficacy Outcome

The secondary efficacy outcomes for this study will be:

- Infarct size parameters assessed by CMR at 72 ± 4 hours post-study drug and 3 months post-study drug
 - Infarct size as a proportion of ventricular volume (INF/VV)
 - Myocardial salvage index (MSI)
 - Absolute myocardial infarction size (INF).
- Proportion of patients with ST-segment resolution at 4 hours post-study drug
- Proportion of patients with persistent arrhythmias at 30 days and 3 months post-study drug
- Measures of cardiac function by CMR at discharge (72 ± 24 hours) and 3 months for the following
 - End-diastolic volume (EDV)
 - End-systolic volume (ESV)
 - Fractional shortening (FS)
 - Ejection fraction (EF)
- Serum levels of troponin calculated as AUC over 48 hours post treatment
- Plasma biomarkers of cardiac injury, inflammation and remodeling out to 3 months of follow up

6.2.2 Secondary Safety Outcome

The secondary safety outcomes for this study will be:

- Incidence of adverse events (AEs)
- Change from baseline in physical examination results, clinical laboratory values, and vital signs values
- Incidence of all cause and cardiac mortality out to 6 months of follow up-to be assessed by phone call to patient or if patient is unavailable, by medical records of physician/investigator

6.2.3 Secondary Pharmacokinetic Outcome

Plasma concentrations of iodide will be assessed and the appropriate PK parameters calculated.

6.3 Exploratory Outcome

The exploratory outcome for this study will be:

- Incidence of newly onset atrial fibrillation during 14 days post-study drug monitoring period

7 STUDY DESIGN

This is a Phase 2A, randomized, double-blind, placebo-controlled, multi-center study that will evaluate the safety, efficacy, and PK of FDY-5301 in patients with acute STEMI undergoing PCI.

Patients will receive either FDY-5301 or volume matched placebo after informed consent is obtained and a STEMI diagnosis has been made based on clinical and electrocardiogram (ECG) findings, within an hour prior to myocardial reperfusion.

A minimum of 80 evaluable patients will be enrolled and randomized in a 1:1:1:1 ratio to receive a single dose of 0.5, 1.0, or 2.0 mg/kg FDY-5301 or placebo.

All patients will have an early and late (3 month) cardiac magnetic resonance (CMR) and 14 days of arrhythmia monitoring and will be followed up for safety and efficacy for up to 6 months. Patients will be monitored in hospital, and return for clinic visits 14 days, 30 days, and 3 months post PCI (Figure 1).

Figure 1: Study Diagram

8 TREATMENTS

The following is a list of the study treatment abbreviations and ordering that will be used in the TFLs.

Study Treatment Name	Treatment Order on TFLs
Placebo	1
0.5 mg/kg FDY-5301	2
1.0 mg/kg FDY-5301	3
2.0 mg/kg FDY-5301	4
Overall FDY-5301	5 (where necessary)

9 SAMPLE SIZE JUSTIFICATION

As this is the first clinical study of FDY-5301 in patients, safety is the primary focus. For this reason, the goal is to expose a limited number of patients to FDY-5301 while still powering the study to detect significant differences in efficacy measures across groups. A total sample size of 80 patients will provide 80% power to detect a 37% reduction in infarct size (INF) / ventricular volume (VV) assuming a standard deviation (SD) of 10%, a 24% increase in MSI assuming a SD of 20% and a 39% reduction in Troponin area under the curve (AUC) with an SD of 60%. Equal variance was assumed among groups with an unbalanced allocation of patients to placebo (n = 20) and overall FDY-5301 treatment groups (n = 60).

10 DEFINITION OF ANALYSIS POPULATIONS

The **Intent-to-treat (ITT)** population will include patients who gave assent, full consent, abbreviated consent or waived consent and were randomized. This is the “full analysis set” of patients. Patients are included in the ITT population according to the treatment assigned.

The **Safety Population** will consist of all patients who received at least 1 dose of study drug (FDY-5301 or Placebo) and have at least 1 postdose safety assessment.

The **Per Protocol (PP)** population will be a subset of the ITT population and will include patients who gave informed assent/consent, were randomized, received any amount of study drug, underwent PCI, and underwent magnetic resonance imaging (MRI) at 72 ± 24 hours and 3 months.

The **PK Population** will consist of all subjects dosed with FDY-5301 and have at least 1 quantifiable postdose PK concentration.

The **PK/PP Population** will consist of all subjects who satisfy the criteria for both the PK and PP population.

All protocol deviations that occur during the study will be considered prior to database lock for their severity/impact and will be taken into consideration when patients are assigned to analysis populations. Details of patient assignment to the analysis populations will be listed.

